2.1.3 Dose Escalation Rules

Pembrolizumab will be administered at a fixed dose of 200 mg IV every 21 days on Day 1 of each cycle.

The starting dose of cabozantinib for subjects in the first cohort will be 40 mg PO once daily for 21 consecutive days of each cycle (Days 1–21). For the second cohort, the dose of cabozantinib will be 60 mg PO once daily. If the starting dose of 40mg is not tolerated (2 or more out of 6 subjects experiencing DLT), then a lower dose of 20 mg will be evaluated.

Once the DLT assessment period has passed, pembrolizumab and/or cabozantinib may be held or dose modified independent of the other agent for adverse events attributed to one but not both drugs. The Principal Investigator should be notified when this occurs.

In addition to any DLTs, other available relevant demographic, adverse event, laboratory, and dose administration data will be reviewed prior to all dose-escalation decisions.

Dose escalation will occur in accordance with the rules:

- A minimum of 3 subjects will be enrolled in each cohort.
- If none of the first 3 DLT-evaluable subjects experiences a DLT, enrollment of the next cohort may proceed.
- If 1 of the first 3 DLT-evaluable subjects experiences a DLT, the cohort will be expanded to a minimum of 6 subjects. If there are no further DLTs in the first 6 DLT-evaluable subjects, enrollment of the next cohort may proceed.
- If 2 or more of the first 6 DLT-evaluable subjects in a cohort experience a DLT, the MTD will have been exceeded and dose escalation will stop. The preceding cohort will also be expanded to a minimum of 6 subjects, unless 6 subjects have already been evaluated at that dose level.
- If the MTD is exceeded at any dose level, the highest dose at which fewer than 2 of 6 DLTevaluable subjects experience a DLT will be declared the MTD.
- If the MTD is not exceeded at any dose level, the highest dose administered in this study will be declared the maximum administered dose.
- Any dose level may be expanded in the absence of a DLT if warranted based on investigator evaluation of non-DLT adverse events, including events occurring after Cycle 1 and events observed in the expansion cohorts.
- To be considered evaluable for dose escalation, subjects must have received at least 1 dose of pembrolizumab and ≥75% of planned dosing of cabozantinib prior to completing the DLT assessment window of 21 days.

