2.1.1 Phase I Dose Escalation

Approximately 6-9 subjects will be enrolled using a standard 3+3 design. Three to six subjects will be enrolled in each dose cohort and receive cabozantinib and pembrolizumab in accordance with the dose escalation rules described below to determine the maximum tolerated dose (MTD) and RP2D (Section 2.1.3). The dose limiting toxicity (DLT) assessment window will be 21 days (Days 1–21 of Cycle 1). If a delayed DLT is observed, the DLT assessment window may be extended after the first administration of pembrolizumab and cabozantinib for all subjects in that cohort and any subsequent dose-escalation cohorts.

Any dose-escalation stage subject who does not complete the DLT assessment window for a reason other than a DLT will be considered non-evaluable for dose escalation decisions, as well as, the MTD assessment and may be replaced by an additional subject at that same dose level.

A subject who has any component of study treatment held during the DLT assessment window for a reason other than a DLT such that administration of the next planned pembrolizumab dose is delayed by more than 7 days and/or $\geq 25\%$ of the planned cabozantinib doses are missed, will be considered non-evaluable for dose-escalation decisions and the MTD assessment and may be replaced by an additional subject at that same dose level.

| Cohort | Pembrolizumab Dose | Cabozantinib Dose |
|--------|-------------------------|-------------------|
| -1 | 200 mg IV every 3 weeks | 20 mg PO daily |
| 1* | 200 mg IV every 3 weeks | 40 mg PO daily |
| 2 | 200 mg IV every 3 weeks | 60 mg PO daily |

* Starting dose level.

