2.1.4 Definition of Maximum Tolerated Dose (MTD)

The Maximum Tolerated Dose (MTD) is defined as the highest dose level with no more than 1 DLT reported in 6 DLT-evaluable subjects.

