8.2.2 Analysis of Safety

Safety will be assessed through summaries of DLTs, adverse events, clinically significant changes in laboratory test results, clinically significant changes in vital signs and ECGs, and exposure to components of study treatment. All subjects who receive any amount of study treatment will be included in the safety analyses.

Adverse event data will be listed by dose cohort. Events occurring on or after treatment on Cycle 1, Day 1 will be summarized by AE term, NCI CTCAE v4.0 grade, and relationship to either pembrolizumab and/or cabozantinib.

Serious adverse events, including deaths, will be listed separately and summarized.

Adverse events leading to treatment discontinuation will be listed.

Adverse events meeting the criteria for DLT will be listed. Subjects who withdraw from the study prior to completing the DLT assessment window for reasons other than a DLT will be considered unevaluable for DLT assessments.

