8.2.5 Sample Size

The proposed study is a single-arm, phase I/II study of pembrolizumab in combination with cabozantinib in subjects with metastatic RCC. We will use a Simon two-stage design for the phase II portion this study based on the primary endpoint of objective response rate. The planned enrollment for this study is approximately 25-55 total subjects, to account for screen failures, in order to achieve 6-9 evaluable subjects in Phase I dose escalation and 20-38 evaluable subjects in Phase II dose expansion. Subjects from the Phase I part of the study who are treated at the RP2D may be included in the efficacy assessments in Stage I of the Phase II part of the study.

Phase I:

Any subject who does not complete the DLT assessment window for any reason other than a DLT will be considered non-evaluable for dose-escalation decisions and MTD and RP2D assessment and will be replaced by an additional subject at that same dose level.

Table 12 describes the probability of not observing any DLTs in 3 subjects, and the probability of observing fewer than two DLTs in 6 subjects for different underlying DLT rates.

| Underlying DLT Rate | Probability of Observing No DLTs in 3 Subjects | Probability of Observing Fewer Than Two DLTs in 6 Subjects |
|---------------------|---|---|
| 0.10 | 0.73 | 0.89 |
| 0.20 | 0.51 | 0.66 |
| 0.33 | 0.30 | 0.36 |
| 0.40 | 0.22 | 0.23 |
| 0.50 | 0.13 | 0.11 |
| 0.60 | 0.06 | 0.04 |

Table 12: Probability of Observing DLTs for Different Underlying DLT Rates

For a given adverse event with a true rate of 10%, 5%, or 1%, the probability of observing at least one such adverse event in a given cohort of 6 subjects is 47%, 26.5%, and 5.8%, respectively.

Phase II:

The Simon's two-stage design will be implemented to test the null hypothesis that $ORR \le 0.20$ versus the alternative that $ORR \ge 0.50$. After the enrollment of 20 evaluable patients in the first stage, the trial will be terminated if 2 or fewer respond. If the trial goes on to the second stage, a total of 38 patients will be studied. If the total number responding is greater than 12, the treatment is considered effective.

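### The 75% cabozantinib evaluability bullet in Section 2.1.3 has no exception for DLTs, so a literal reading drops some early DLTs from the escalation and MTD counts

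*Combined protocol and SAP*

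**What the plan says.** Section 2.1.3 ends its list of escalation rules with an affirmative test of evaluability: "To be considered evaluable for dose escalation, subjects must have received at least 1 dose of pembrolizumab and" at least "75% of planned dosing of cabozantinib prior to completing the DLT assessment window of 21 days". The test is on exposure alone. The reason for a shortfall plays no part.

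Four other sections bring the reason in:

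- **Section 2.1.1, non-completion.** A dose-escalation subject "who does not complete the DLT assessment window for a reason other than a DLT will be considered non-evaluable for dose escalation decisions".
- **Section 2.1.1, missed doses.** This paragraph opens "A subject who has any component of study treatment held during the DLT assessment window for a reason other than a DLT such that" and then names a pembrolizumab delay of more than 7 days or 25% or more of cabozantinib doses missed.
- **Section 5.8.** Repeats both rules, each with the same restriction to non-DLT reasons.
- **Section 8.2.2.** Subjects who withdraw "prior to completing the DLT assessment window for reasons other than a DLT will be considered unevaluable for DLT assessments".
- **Section 8.2.5.** "Any subject who does not complete the DLT assessment window for any reason other than a DLT will be considered non-evaluable for dose-escalation decisions".

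The counts that use evaluability are the 0-of-3, 1-of-3 and 2-of-6 bullets in Section 2.1.3 and the MTD definition in Section 2.1.4: "highest dose level with no more than 1 DLT reported in 6 DLT-evaluable subjects". The RP2D rule in Section 2.1.5 speaks of subjects, without the evaluability qualifier.

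**The concern.** A DLT is often the reason that dosing stops. An exposure minimum that ignores the reason therefore tends to exclude the subjects whose toxicity came early and was treatment-limiting. Section 2.1.2 itself lists a combined transaminase and bilirubin elevation that requires permanent discontinuation. A subject with that event early in Cycle 1 cannot reach the 75% minimum.

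The bullet is the only affirmative statement of who is evaluable, and it sits in the same list as the escalation rules, so a reader would naturally use it as the definition. With 3 to 6 subjects per dose level, one uncounted DLT can decide whether a cohort expands, escalates or stops, and the error runs in one direction: towards a higher declared MTD. The MTD and RP2D counts could also differ, because Section 2.1.5 does not restrict its count to evaluable subjects.

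**Working it through.** **Step 1: doses needed.** Section 2.1.3 plans cabozantinib "PO once daily for 21 consecutive days of each cycle", so 21 doses fall in the window. 0.75 × 21 = 15.75, so 16 doses are needed and 5 may be missed. Under Sections 2.1.1 and 5.8, 25% of 21 is 5.25, so 6 missed doses (15 taken) trigger their rule. The two thresholds coincide: 16 doses passes and 15 fails. The missing DLT exception is the only difference in the cabozantinib dose rule.

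**Step 2: who is affected.** A subject who stops cabozantinib for a DLT after 15 or fewer doses, and does not resume in time to reach 16, fails the Section 2.1.3 bullet. None of the other four sections makes that subject non-evaluable. A DLT hold of up to 5 days, or a DLT after the 16th dose, does no harm under either rule.

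**Step 3: reproduce the plan's figure.** Table 12 gives P(fewer than 2 DLTs in 6) = (1−q)^6 + 6q(1−q)^5.

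- q = 0.33: 0.358 (Table 12: 0.36).
- q = 0.40: 0.233 (Table 12: 0.23).

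All 12 cells of Table 12 reproduce after rounding.

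**Step 4: literal reading.** Let q be the true DLT rate and e the share of DLT subjects dropped and replaced. The DLT rate among evaluable subjects is then

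r = q(1−e) / [(1−q) + q(1−e)].

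Example: q = 0.33, e = 0.25 gives r = 0.2475 / (0.67 + 0.2475) = 0.2475 / 0.9175 = 0.270.

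The documents give no value for e, so a range is shown. The top value is 15/21 = 0.714. It assumes DLT onset uniform over 21 days, the dose on the day of onset taken, and a stop then without resumption.

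| True rate q | Share dropped e | Rate among evaluable r | P(fewer than 2 of 6) |
|---|---|---|---|
| 0.33 | 0 | 0.330 | 0.358 |
| 0.33 | 0.25 | 0.270 | 0.488 |
| 0.33 | 0.50 | 0.198 | 0.661 |
| 0.33 | 15/21 | 0.123 | 0.837 |
| 0.40 | 0 | 0.400 | 0.233 |
| 0.40 | 0.25 | 0.333 | 0.351 |
| 0.40 | 0.50 | 0.250 | 0.534 |
| 0.40 | 15/21 | 0.160 | 0.753 |

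**Step 5: the full 3+3 rule.** The Table 12 column is not the chance that a dose level is cleared. That chance is (1−r)^3 + 3r(1−r)^2 × (1−r)^3. At q = 0.33 it is 0.434 when every DLT counts, and 0.557, 0.714 and 0.865 for e = 0.25, 0.50 and 15/21. The shift has the same direction and a similar size.

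**The case against.** The best defence is that the bullet is shorthand. Sections 2.1.1 and 5.8 state the same dose threshold with the DLT exception, the design is described as a standard 3+3, and an experienced team would count the DLT. That is probably the intent. It does not say which sentence governs when they disagree, and the bullet is the one placed beside the counting rules.

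Several narrower points stand in part:

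- **Reach of the conflict.** Sections 8.2.2 and 8.2.5 concern withdrawal or non-completion and name no dose minimum, so the direct contradiction is with Sections 2.1.1 and 5.8. The other two show that the plan otherwise excepts DLTs consistently.
- **Terminology.** The bullet defines evaluability for dose escalation, while the counts refer to DLT-evaluable subjects, a term with no separate definition. The effect on the MTD assumes that the two mean the same, which is the natural reading.
- **Magnitude.** The share dropped has no source in the documents, and the replacement text covers only non-DLT reasons. Several DLT definitions require the event to persist for days, so stopping at onset is not assured. The 71% row is a bound, not an expectation.
- **Safeguards.** Section 2.1.3 requires other adverse event, laboratory and dosing data to be reviewed before each escalation decision, and Section 8.2.2 lists every event that meets the DLT criteria. The event would be seen. On its wording, the RP2D rule in Section 2.1.5 would still count it.

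These points limit the likely harm. They do not settle the formal MTD count.

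**Conclusion.** The concern holds. Section 2.1.3 contradicts Sections 2.1.1 and 5.8 directly, departs from the approach of Sections 8.2.2 and 8.2.5, and no passage gives precedence. If the bullet governs, DLTs that end cabozantinib before the 16th dose leave the escalation and MTD counts and the MTD is biased upward. If the other sections govern, the change is zero and Table 12 stands.

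The probabilities above are illustrative. They rest on the literal reading, on the two evaluability terms meaning the same, on replacement of dropped subjects, and on an assumed share affected. DLT, MTD and RP2D are secondary objectives, so the primary response-rate test is not directly altered. This should be fixed because the written rule ought to give one answer. Confidence in the contradiction is high; the size of its effect cannot be determined from the documents.

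**What to change.** Reconcile Section 2.1.3 with Sections 2.1.1, 5.8, 8.2.2 and 8.2.5 by applying the exposure minimum only to subjects without a DLT. Suggested wording: *Any treated subject with a DLT in the assessment window is DLT-evaluable. A subject without a DLT is DLT-evaluable only if at least 1 dose of pembrolizumab and at least 75% of planned cabozantinib were received in the window.* This also supplies the missing definition of DLT-evaluable. A cross-reference to Section 2.1.1 would be optional tidying.

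The cost is one clause. No dose, treatment rule, visit or sample size changes.

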2.1.4 Definition of Maximum Tolerated Dose (MTD)

The Maximum Tolerated Dose (MTD) is defined as the highest dose level with no more than 1 DLT reported in 6 DLT-evaluable subjects.

2.1.5 Definition of Recommended Phase 2 Dose (RP2D)

The Recommended Phase 2 Dose (RP2D) of cabozantinib will be selected based on the clinical data and will not exceed the MTD. If < 2/6 subjects experience a DLT at 60 mg daily during dose escalation, then 60 mg daily will be considered the RP2D. If \geq 2/6 subjects experience DLTs at 60 mg daily, and \leq 1/6 subjects experience a DLT at 40 mg daily, then 40 mg daily will be considered the RP2D. The Principal Investigator, in consultation with other investigators, will continue to evaluate the safety data accumulated during the phase II dose expansion part of the study and may amend the RP2D with further experience.

2.1.6 Intra-Subject Dose Escalation

There will be no dose reduction or escalation of pembrolizumab, which is to be administered at a fixed dose of 200 mg IV every 21 days.

Intra-subject dose escalation of cabozantinib to a higher dose level will be allowed if all of the following conditions are met:

- One or fewer of the first 3 DLT-evaluable subjects, or fewer than 2 of the first 6 DLTevaluable subjects experience a DLT at the higher dose level cohort.
- The subject has completed at least 3 cycles at their originally assigned dose level.
- The subject has not experienced a DLT or an adverse event occurring outside the DLT window that would otherwise meet the definition of a DLT.
- The subject is clinically stable with no decrement in performance status.
- The Principal Investigator has approved the dose escalation.
- The overall benefit/risk balance favors continued treatment, in the opinion of the investigator.

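### Intra-subject escalation is open to a cabozantinib dose with 1 DLT in 3 subjects, a result that Section 2.1.3 leaves unresolved until the cohort is expanded

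*Combined protocol and SAP*

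**What the plan says.** Section 2.1.6 lists conditions that must all be met before a subject's cabozantinib dose is raised. The only one about results at the higher dose is that "One or fewer of the first 3 DLT-evaluable subjects, or fewer than 2 of the first 6" evaluable subjects there have had a DLT. The others concern the subject's own course (for example "The subject has completed at least 3 cycles at their originally assigned dose level", no DLT or equivalent event, clinical stability), a sign-off ("The Principal Investigator has approved the dose escalation") and the investigator's view of benefit and risk.

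Section 2.1.3 governs the cohorts:

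- 0 of 3: "If none of the first 3 DLT-evaluable subjects experiences a DLT, enrollment of the next cohort may proceed".
- 1 of 3: "If 1 of the first 3 DLT-evaluable subjects experiences a DLT, the cohort will be expanded to a minimum of 6 subjects". After that, "If there are no further DLTs in the first 6 DLT-evaluable subjects, enrollment of the next cohort may proceed".
- 2 or more of 6: "If 2 or more of the first 6 DLT-evaluable subjects in a cohort experience a DLT, the MTD will have been exceeded".

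Section 2.1.4 defines the MTD as the "highest dose level with no more than 1 DLT reported in 6 DLT-evaluable subjects". Section 4.2.2.2 restates the cohort rule as no DLT in 3 or at most 1 in 6. Section 2.1.5 caps the RP2D at the MTD, but that cap is not applied to intra-subject escalation.

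**The concern.** The plan uses two standards for the same evidence at the same dose. Under Section 2.1.3 a 1/3 result does not settle whether the dose is tolerated, and three more subjects are needed to find out. Under Section 2.1.6 it already satisfies the DLT condition for moving other subjects up to that dose, while the question is still open.

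Those at risk are subjects who have tolerated a lower dose for at least three cycles without a DLT. They could be moved to a level that the trial then declares above the MTD. With a starting dose of 40 mg and a top cohort of 60 mg, the issue mainly concerns the 40 mg to 60 mg step.

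**Working it through.** **Inputs.** The decision rules are those of Sections 2.1.3 and 2.1.6. The true DLT rates p are those of Table 12 (Section 8.2.5). DLTs are taken as independent with a common rate.

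**The plan's own figures first.** Table 12 follows from P(0/3) = (1−p)³ and P(<2/6) = (1−p)⁶ + 6p(1−p)⁵. At p = 0.33 these give 0.67³ = 0.301 (printed 0.30) and 0.358 (printed 0.36). All twelve entries reproduce to two decimals.

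**The result in dispute.**

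- Exactly 1 of 3: A = 3p(1−p)². At p = 0.33, 3 × 0.33 × 0.4489 = 0.444.
- Given 1/3, at least one more DLT in the next three, which makes at least 2/6 and fails Section 2.1.3: B = 1 − (1−p)³. At p = 0.33, 1 − 0.301 = 0.699.
- Both: A × B. At p = 0.33, 0.444 × 0.699 = 0.311.
- Three-subject limb of 2.1.6 met: P(≤1/3) = (1−p)³ + A.
- Cleared under 2.1.3: (1−p)³ + A(1−p)³.

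| True DLT rate | A: exactly 1/3 | B: dose then fails, given 1/3 | A × B | 2.1.6 three-subject limb met | Cleared under 2.1.3 |
|---|---|---|---|---|---|
| 0.10 | 0.24 | 0.27 | 0.07 | 0.97 | 0.91 |
| 0.20 | 0.38 | 0.49 | 0.19 | 0.90 | 0.71 |
| 0.33 | 0.44 | 0.70 | 0.31 | 0.75 | 0.43 |
| 0.40 | 0.43 | 0.78 | 0.34 | 0.65 | 0.31 |
| 0.50 | 0.38 | 0.88 | 0.33 | 0.50 | 0.17 |
| 0.60 | 0.29 | 0.94 | 0.27 | 0.35 | 0.08 |

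The last two columns differ by A × B, apart from rounding. That gap is the set of outcomes in which 2.1.6 permits escalation to a dose that 2.1.3 goes on to reject.

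**Does the three-cycle minimum close the gap?** Three cycles are 3 × 21 = 63 days. Take the fastest fully sequential case: each group of three starts together as soon as the previous 21-day window closes. Counting from Day 1 of the last 40 mg subject, that window closes on day 21, the first three at 60 mg finish on day 42, and the expansion finishes on day 63. Day 63 is when that last 40 mg subject completes three cycles; subjects enrolled earlier get there sooner.

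Actual accrual is likely to be slower. Section 1.0 plans 25 to 55 subjects over 3 years, which is 25/36 = 0.69 to 55/36 = 1.53 per month. If that average held in Phase I (an assumption, since no Phase I rate is given), three more subjects would take 3/1.53 = 2.0 to 3/0.69 = 4.3 months. The minimum may sometimes outlast the expansion, but nothing guarantees it.

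**Literal reading.** Since either limb suffices, a dose with 1/3 that later reaches 2/6 or more still meets the first limb. Nothing in 2.1.6 withdraws the permission.

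**The case against.** The strongest reply is that the two sections answer different questions. Section 2.1.3 decides whether to open the next cohort and whether the MTD has been passed. At 1/3 it does not suspend the dose; it enrols at least three more subjects there. Moving a subject to that same level, not above it, could be a deliberate choice with its own threshold. The candidates are also selected for tolerance, and escalation needs Principal Investigator approval and a favourable benefit/risk view. Section 2.1.3 also calls for review of other safety data before dose-escalation decisions, which may be read to cover these.

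Much of this is fair. Further dosing at 1/3 is part of any 3+3 design, and the two rules can both be followed. But the three added subjects are cohort subjects under DLT observation, and their results decide the dose. Subjects escalated under 2.1.6 have no such role. The safeguards are matters of judgement, and none makes escalation depend on the higher cohort being resolved. If a different threshold was intended, the plan does not say so or give a reason.

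Three points limit the size. The values in column B are conditional on 1/3 having occurred. The joint values in A × B overstate actual exposure, because a lower-dose subject must also be eligible and approved. Phase I plans only 6 to 9 subjects (Section 2.1.1), so few are affected. In addition, Section 5.2.1.3.2 provides for patients already beyond 35 cycles at the October 2020 version, which suggests that dose escalation may be over. The documents do not confirm this, and the rule stands in the current text.

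**Conclusion.** The concern holds. Section 2.1.6 accepts 1/3 at the higher dose, whereas Sections 2.1.3 and 4.2.2.2 clear a dose only at 0/3 or at most 1/6. At true DLT rates of 0.20 to 0.40, the probability that 2.1.6 opens at 1/3 and the dose then fails 2.1.3 is 0.19 to 0.34; at 0.10 it is 0.07.

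The inconsistency is visible from the wording alone. The probabilities show its size and rest on independent DLTs with a common rate. How many subjects would be affected depends on Phase I accrual and on investigator decisions, neither of which the documents fix. The point should be corrected because it concerns subject safety and is cheap to settle, though it touches few subjects.

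**What to change.** Reconcile Section 2.1.6 with Section 2.1.3 so that both rest on one stated criterion for when a dose level is cleared. The text should also make plain what happens to the permission in 2.1.6 if the higher dose is later found to exceed the MTD. If the different threshold is intended, say so and give the justification. Which criterion applies is for the sponsor to decide.

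The cost is a wording amendment, with no effect on sample size or analysis. If the reconciled text made escalation wait for the expanded cohort, some intra-subject escalations would be delayed by the time needed to enrol three subjects and complete their 21-day windows. The documents do not allow that delay to be fixed more closely.
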